#### **Exploratory Endpoints:**

1. Genetic alterations
2. MRI Imaging changes

### **13.3 Sample Size, Accrual Rate and Study Duration**

The total accrual for this phase II trial will be 26 patients in order to achieve 24 evaluable patients. The estimated accrual rate will be approximately 1 patients per month for this protocol. Twenty-six patients will be accrued within 24-28 months. Based on 6 months of follow-up, the total study duration will be 36 months. Both men and women of all races and ethnic groups are eligible for this trial. Every effort will be made to include patients from minority populations.

### **13.4 Stratification Factors**

NA

### **13.5 Interim Monitoring Plan**

NA

### **13.6 Analysis of Primary Endpoints**

The goal will be to enroll 24 patients. The primary endpoint is the rate of 6 month PFS. The trial will distinguish between 6 month PFS rates of 26% vs. 52%. The historical control of 6 month PFS is based on a recent meta-analysis showing a PFS-6 of 26% in recurrent Grade II/III meningiomas and other studies in this patient population. If at least 10 patients demonstrate 6 month PFS, among the 24 evaluable patients, the agent will be considered worthy of further study, yielding at least 88% power to detect a true 6 month PFS rate of at least 52%, using an exact binomial test with a one-sided significance level of 0.1, against the null hypothesis of 26% 6-month PFS.

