## 5. TREATMENT PLAN

### 5.1 Treatment Regimen

Pembrolizumab will be administered every 3 weeks, with 21 consecutive days defined as a treatment cycle. Treatment will be administered on an outpatient basis. Reported adverse events and potential risks are described in Section 7. Appropriate dose modifications are described in Section 6. No investigational or commercial agents or therapies other than those described below may be administered with the intent to treat the participant's malignancy.

The treatment to be used in this trial is outlined below in the table below.

Table 2: Dose of Pembrolizumab

Drug	Dose/Potency	Dose Frequency	Route of Administration	Regimen/Treatment Period	Cycle Length
Pembrolizumab	200 mg	Q3W	IV infusion	Day 1 of each 3 week cycle	3 weeks

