#### 11.2 Definitions

Evaluable for objective response. Only those participants who have measurable CNS disease present at baseline, have received at least one cycle of therapy, and have had their disease re-evaluated will be considered evaluable for target disease response. These participants will have their response classified according to the definitions stated below. (Note: Participants who exhibit objective disease progression prior to the end of cycle 1 will also be considered evaluable.)

Evaluable non-measurable evaluable disease. Participants who have lesions present at baseline that are evaluable but do not meet the definitions of measurable disease, have received at least one cycle of therapy, and have had their disease re-evaluated will be considered evaluable for non-target disease. The response assessment is based on the presence, absence, or unequivocal progression of the lesions.

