### **13.2 Endpoints**

#### **Primary Endpoints:**

The primary endpoint is progression-free survival at 6 months (PFS6). PFS6 is defined as not having progressive disease or death within six months of the first day of treatment. Contrast-enhanced cranial magnetic resonance imaging (MRI) will be performed every 6 weeks. Standard response criteria will be used (see [Section 11.0](#)).

All patients meeting the eligibility criteria that have signed the consent form and have begun treatment will be considered evaluable for the analysis of primary endpoint.

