## **13.9 Reporting and Exclusions**

### **13.9.1 Evaluation of Toxicity**

All participants who have received at least one dose of study medication will be evaluable for toxicity from the time of their first treatment.

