### **13.9.2 Evaluation of the Primary Efficacy Endpoint**

To be included in the assessment of the primary objective, patients need to receive at least one cycle. If systemic progression occurs prior to the 6 week CNS response timepoint, patient will still be included in the analysis of primary objective.

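### Sections 13.2 and 13.9.2 set different entry conditions for the primary analysis, and on the 21-day reading of a cycle the second can exclude early PFS6 failures; the cut-off is also printed for 24 patients only

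*Combined protocol and SAP*

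**What the plan says.** **Analysis set.** Section 13.2, under Primary Endpoints, states: "All patients meeting the eligibility criteria that have signed the consent form and have begun treatment will be considered evaluable". It defines the outcome from the start of treatment: "PFS6 is defined as not having progressive disease or death within six months of the first day of treatment". Section 13.9.2, on the same objective, states: "To be included in the assessment of the primary objective, patients need to receive at least one cycle". It then makes one provision for early failure: "If systemic progression occurs prior to the 6 week CNS response timepoint, patient will still be included in the analysis of primary objective". No section says which condition governs.

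**What a cycle is.** Section 5.1 gives the regimen "with 21 consecutive days defined as a treatment cycle", with one infusion on day 1. Section 13.9.1, immediately before 13.9.2, uses a different unit for safety: "All participants who have received at least one dose of study medication will be evaluable for toxicity". Section 11.2 also asks for one cycle, for response evaluability, and then adds: "Participants who exhibit objective disease progression prior to the end of cycle 1 will also be considered evaluable".

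**Decision rule.** Section 13.6 sets a null rate of 26%, an alternative of 52%, an exact binomial test at one-sided 0.1 and power of at least 88%. The only count it prints is: "If at least 10 patients demonstrate 6 month PFS, among the 24 evaluable patients, the agent will be considered worthy of further study". Section 13.3 accrues 26 patients to obtain 24 evaluable. Section 4.1 cancels the registration of anyone not treated, without saying whether that person counts toward the 26.

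**The concern.** The trial has one arm and compares PFS6 with a fixed 26% benchmark, so no control group absorbs the effect of leaving patients out. A condition that can be failed by dying or progressing soon after the first infusion selects on the outcome. If 13.9.2 governs and a cycle means 21 days, some patients who are failures under 13.2 leave the denominator. The estimate then rises for a reason that has nothing to do with the drug.

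The second matter is smaller. Under 13.2 the evaluable number could be 24, 25 or 26, or could fall below 24, but a count is printed for 24 alone. In an open-label trial (section 8.5), neither the analysis set nor the count should be left to be chosen once outcomes are known.

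**Working it through.** **1. The two conditions side by side**

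| Event in cycle 1 | 13.2 | 13.9.2, cycle = 21 days | 13.9.2, cycle = one infusion |
|---|---|---|---|
| Death | Counted, failure | May be excluded; no exception stated | Counted, failure |
| Intracranial or clinical progression | Counted, failure | May be excluded; no exception stated | Counted, failure |
| Systemic progression | Counted, failure | Kept explicitly | Counted, failure |
| Stop for toxicity only | Counted; outcome from follow-up (5.13, 12.1.3) | May be excluded | Counted |

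I read systemic progression as extracranial, because 13.9.2 sets it against a CNS assessment. Clinical worsening, and failure to return because of death or deterioration, are both progression under 11.3.1.1.

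Three places favour the 21-day reading: the definition in 5.1; the separate use of a dose as the unit in 13.9.1; and the exception in 11.2 for progression before cycle 1 ends, which would hardly be needed if a cycle were complete at the infusion. None of them defines when a cycle has been received.

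**2. Size of the upward shift**

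With *s* successes among *n* patients who began treatment, and *k* early failures removed, the estimate moves from *s/n* to *s/(n − k)*, a factor of *n/(n − k)*. The documents do not give *k*, so these are illustrations.

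- *n* = 26, *k* = 2, *s* = 10: 10/26 = 38.5% becomes 10/24 = 41.7% (factor 26/24 = 1.083). With the exact test at the actual number, p goes from 0.113 to 0.069, across the 0.10 line.
- *n* = 24, *k* = 2, *s* = 9: 9/24 = 37.5% becomes 9/22 = 40.9%. The exact p goes from 0.147 to 0.092, again across the line.

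Such reversals are confined to borderline counts. Exactly 10 successes in 26 has probability 0.061 at a true rate of 26% and also 0.061 at 52%.

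**3. The cut-off**

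Inputs from 13.6: null 0.26, alternative 0.52, one-sided 0.10, single stage (13.1 plans no interim analysis). For cut-off *r* among *n*:

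- type I error = Σ (x = r to n) C(n, x) · 0.26^x · 0.74^(n − x)
- power = Σ (x = r to n) C(n, x) · 0.52^x · 0.48^(n − x)

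The plan's own figure comes first: at *n* = 24, *r* = 10, type I error is 0.069 and power 0.888, as stated. At *r* = 9 type I error is 0.147, so 10 is the smallest valid count.

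| Evaluable n | Cut-off | Type I error | Power | Within 0.10? |
|---|---|---|---|---|
| 22 | ≥9 | 0.092 | 0.895 | yes |
| 23 | ≥9 | 0.118 | 0.926 | no |
| 23 | ≥10 | 0.052 | 0.848 | yes |
| 24 | ≥10 | 0.069 | 0.888 | yes |
| 25 | ≥9 | 0.179 | 0.965 | no |
| 25 | ≥10 | 0.089 | 0.920 | yes |
| 26 | ≥10 | 0.113 | 0.943 | no |
| 26 | ≥11 | 0.052 | 0.882 | yes |

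The printed count therefore carries over to 23 and 25 but not to 26. At 23 it is valid, but power falls below the stated 88%.

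**The case against.** **On the analysis set.** Treatment is one infusion on day 1, so a patient who has had it can fairly be said to have received that cycle. On that reading the sections nearly coincide. The plan also tends to keep early failures: 11.2 and 11.4.1 retain patients who progress in cycle 1, 11.3.1.1 treats death before evaluation as progression, and 13.9.2 itself keeps early systemic progression. This has weight, and it is why the 21-day reading cannot be called settled. But 11.2 and 11.4.1 govern response evaluability rather than PFS6, and 11.3.1.1 classifies an event without saying who enters the analysis. The exception written into 13.9.2 covers one kind of early failure and is silent on the rest.

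**On direction.** Removing failures can only raise the estimate, but the same condition might also remove a patient who stopped for toxicity in cycle 1 and later proved a success. With 24 treated and 10 successes, one of them that patient, 10/24 = 41.7% becomes 9/23 = 39.1%, and p goes from 0.069 to 0.118. The net direction over all possible exclusions is therefore not fixed. This stands, and it is a further reason to have one set.

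**On the cut-off.** A reader might infer that the trial runs at a type I error of 0.113. The documents do not support that. Section 13.6 ties the count of 10 to 24 evaluable patients and names an exact test at 0.1; nothing tells the analyst to apply 10 to 26. Nor can that excess be added to the 26-patient reversal above. If the exact test governs at the actual number, the error stays within 0.10; if the bare count of 10 governs, 10 of 26 and 10 of 24 both pass and no reversal occurs.

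**Conclusion.** The point holds for the analysis set. Two sections give different entry conditions for one primary analysis. On the 21-day reading of a cycle, 13.9.2 can exclude patients who are failures by the plan's own definition, and excluding them biases PFS6 upward. The shift is modest, about three percentage points for two such patients in the examples (38.5% to 41.7%; 37.5% to 40.9%), and it changes the conclusion only near the boundary. This rests on the 21-day reading, which is favoured but not established, and on early non-systemic failures occurring, for which the documents give no rate. If a cycle means one infusion, little remains beyond a wording mismatch.

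The cut-off is a secondary clarification. The 24-patient design is correct and the count of 10 is still valid at 25. Only if it were carried over to 26 would the error exceed 0.10, by 0.013, and the plan does not instruct that. The whole is worth fixing because it concerns the trial's only go/no-go rule and costs very little.

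**What to change.** 1. In 13.9.2, delete the one-cycle condition and refer to 13.2, so that all eligible, consented patients who began treatment form the only primary-analysis population. The sentence on systemic progression then becomes unnecessary; if it is kept, extend it to death and to intracranial and clinical progression.
2. In 13.6, state that the exact one-sided 0.10 test applies at the actual evaluable number, and list the cut-offs: at least 9 of 22; at least 10 of 23, 24 or 25; at least 11 of 26. Note that power at 23 is 0.848, below the stated 88%.

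The cost is a few sentences in two sections, with no added patients or visits. The downside is a slightly more conservative estimate, and a bar of 11 rather than 10 if all 26 patients are evaluable; power at that bar is 0.882, so both stated properties are kept.

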### **13.7 Analysis of Secondary Endpoints**

Safety and Tolerability: All adverse events recorded during the trial will be summarized for all patients having received one or more doses of pembrolizumab. The proportions of patients with grade-3 or higher hematologic toxicities or grade-3 or higher neurologic toxicities will be presented with 90% exact binomial confidence intervals. The incidence of events that are new or worsening from the time of first dose of treatment will be summarized according to system organ class and/or preferred term, severity (based on CTCAE grade), type of adverse event, and relation to study treatment. Deaths reportable as SAEs and non-fatal serious adverse events will be listed by patient and tabulated by primary system organ class, and type of adverse event.

Overall Survival: The distributions of overall survival will be summarized using the method of Kaplan-Meier. The follow-up of patients who are alive at the time of analysis will be censored at the date of last assessment of vital status. Median OS will be presented and accompanied by 90% confidence intervals estimated using log(-log(survival)) methodology. Survival point estimates at 3 and 6 months will also be presented with confidence intervals.

Intracranial/Extracranial Response: Contrast-enhanced cranial magnetic resonance imaging (MRI) will be performed every 6 weeks. The proportion of patients with intracranial response (CR, PR or SD by RANO) will be presented with a two-sided, 90% exact binomial confidence interval.

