  - For **Grade 2** events, treat with corticosteroids.
  - For **Grade 3-4** events, treat with systemic corticosteroids.
  - When symptoms improve to Grade 1 or less, steroid taper should be started and continued over no less than 4 weeks.
- **Cerebral Edema**

Due to the immunologic nature of pembrolizumab administration, cerebral edema could theoretically result as a consequence of pembrolizumab administration due to immune infiltration of the brain. Symptoms related to cerebral edema may include headache or neurologic deficit that is either new or worsened. Patients with any signs or symptoms of cerebral edema should be treated as clinically appropriate including initiation or increased systemic corticosteroid dosing, treatment with an osmotic diuretic or surgical decompression. Subsequent pembrolizumab dosing should be immediately interrupted if significant clinical symptoms attributable to cerebral edema develop. Treatment with additional pembrolizumab doses may only be re-initiated if clinically significant symptoms attributable to cerebral edema have resolved to grade  $\leq 1$  or pre-treatment baseline. Patients who develop CTCAE 4.0 grade-4 cerebral edema attributable to pembrolizumab administration should not receive further pembrolizumab doses and should discontinue study therapy.

Recommendations to manage irAEs not detailed elsewhere in the protocol are detailed in Table 4.

Table 4 Dose Modification and Toxicity Management Guidelines for Immune-related AEs Associated with Pembrolizumab

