## 7. ADVERSE EVENTS: LIST AND REPORTING REQUIREMENTS

An adverse event is defined as any untoward medical occurrence in a patient or clinical investigation subject administered a pharmaceutical product and which does not necessarily have to have a causal relationship with this treatment. An adverse event can therefore be any unfavorable and unintended sign (including an abnormal laboratory finding, for example), symptom, or disease temporally associated with the use of a medicinal product or protocol-specified procedure, whether or not considered related to the medicinal product or protocol-specified procedure. Any worsening (i.e., any clinically significant adverse change in frequency and/or intensity) of a preexisting condition that is temporally associated with the use of the Merck's product, is also an adverse event.

Changes resulting from normal growth and development that do not vary significantly in frequency or severity from expected levels are not to be considered adverse events. Examples of this may include, but are not limited to, teething, typical crying in infants and children and onset of menses or menopause occurring at a physiologically appropriate time. Merck product includes any pharmaceutical product, biological product, device, diagnostic agent or protocol-specified procedure, whether investigational (including placebo or active comparator medication) or marketed, manufactured by, licensed by, provided by or distributed by Merck for human use.

Adverse events may occur during the course of the use of Merck product in clinical trials or within the follow-up period specified by the protocol, or prescribed in clinical practice, from overdose (whether accidental or intentional), from abuse and from withdrawal.

Adverse events may also occur in screened subjects during any pre-allocation baseline period as a result of a protocol-specified intervention, including washout or discontinuation of usual therapy, diet, placebo treatment or a procedure. Progression of the cancer under study is not considered an adverse event unless it is considered to be drug related by the investigator.

All adverse events will be recorded from the time of patient registration through 30 days following cessation of treatment and at each examination on the Adverse Event case report forms/worksheets. The reporting timeframe for adverse events meeting any serious criteria is described in section 7.3.

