### **7.3 Immediate Reporting of Adverse Events to the Overall PI and to Merck**

### 7.3.1 Serious Adverse Events

A serious adverse event is any adverse event occurring at any dose or during any use of Merck's product that:

- Results in death;
- Is life threatening;
- Results in persistent or significant disability/incapacity;
- Results in or prolongs an existing inpatient hospitalization;
- Is a congenital anomaly/birth defect;
- Is a new cancer (that is not a condition of the study);
- Is associated with an overdose;
- Is another important medical event

Refer to Table 6 below for additional details regarding each of the above criteria.

Any serious adverse event, or follow up to a serious adverse event, including death due to any cause other than progression of the cancer under study that occurs to any subject from the time of patient registration through 90 days following cessation of treatment, or the initiation of new anti-cancer therapy, whichever is earlier, whether or not related to Merck product, must be reported within 24 hours to the Overall PI and within 2 working days to Merck Global Safety.

Non-serious Events of Clinical Interest will be forwarded to Merck Global Safety and will be handled in the same manner as SAEs.

Additionally, any serious adverse event, considered by an investigator who is a qualified physician to be related to Merck product that is brought to the attention of the investigator at any time outside of the time period specified in the previous paragraph also must be reported immediately to the Overall PI and to Merck.

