### 11.3.3 Study Continuation Beyond Initial Progressive Disease

Immunotherapeutic agents such as pembrolizumab may produce antitumor effects by potentiating endogenous cancer-specific immune responses which may manifest as initial worsening of enhancement and edema on MRI or CT scans (i.e. pseudo-progression). In addition, the response patterns seen with immunotherapeutics may extend beyond the typical time course of responses seen with cytotoxic agents, and can manifest a clinical response after an initial increase in tumor burden or even the appearance of new lesions. For these reasons, the immune-related response criteria (irRC) have endorsed continuation of study therapy beyond initial radiographic evidence of progression for clinically stable patients undergoing immune based therapies.

Therefore, the following adaptations will be used to assess response for patients treated on this study:

**Potential Pseudo-progression:** If radiologic imaging shows initial PD, subjects who are not experiencing significant clinical decline, may be allowed to continue study treatment for up to three months. Patients who have radiographic evidence of progression after up to three months (as defined by progression as in 11.3.1.1), or who decline significantly at anytime, will be classified as progressive with the date of disease progression back-dated to the first date that the subject met criteria for progression and such subjects will be discontinued from study therapy. Three months is the most common timeframe for pseudo-progression observed among patients with advanced melanoma or other solid tumors treated with PD-1/PD-L1 immune checkpoint blockade.

Among patients on this study with initial radiographic PD, tumor assessment should be

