repeated regularly in order to confirm PD with the option of continuing treatment as described below while awaiting radiologic confirmation of progression. If repeat imaging shows a stabilization or reduction in the tumor burden compared to the initial scan demonstrating PD, treatment may be continued / resumed. If repeat imaging after up to three months confirms progressive disease, then the date of disease progression will be the first date the subject met criteria for progression and subjects will be discontinued from study therapy. Subjects who have confirmed disease progression will discontinue study medication and enter the follow up/survival phase of the study. In determining whether or not the tumor burden has increased or decreased, investigators should consider all target lesions as well as non-target lesions.

**Tumor Enhancement to Define Progression:** RANO expanded the previously utilized Macdonald criteria to include the development of “significantly” increased T2 or FLAIR abnormality in the definition of progressive disease because such changes can be a major component defining radiographic progression following therapeutic use of VEGF/VEGFR-targeting therapeutics which are known to elicit potent anti-permeability changes that limit contrast uptake. However, immune based therapies are expected to be associated with inflammatory changes that may include edema. Therefore, our study will define radiographic progressive disease by assessment of enhancing tumor burden only and will not include assessment of T2 or FLAIR changes as outlined in RANO because:

- There is no expectation that immunotherapy agents including PD-1 inhibitors will falsely diminish enhancing tumor burden as has been noted with anti-angiogenic therapies; and
- Immune based therapies are expected to induce inflammatory responses which may be associated with increased edema and T2/FLAIR changes. Such radiographic finding may inaccurately be interpreted to represent tumor progression (i.e. pseudoprogression).

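### The only planned death listing (Section 13.7) leaves out deaths attributed to progression, so a fatal immune-related event given that cause would be missing from it

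*Combined protocol and SAP*

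**What the plan says.** Section 13.7 (safety and tolerability) plans that "All adverse events recorded during the trial will be summarized for all patients having received one or more doses of pembrolizumab". For deaths it plans that "Deaths reportable as SAEs and non-fatal serious adverse events will be listed by patient", with tabulation by organ class and type of event. No other listing of deaths is described.

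Two rules decide which deaths reach that listing:

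- Section 7.3.1 requires SAE reports "including death due to any cause other than progression of the cancer under study", from registration to 90 days after treatment stops or the start of new anti-cancer therapy, whichever is earlier.
- The introduction to Section 7 says: "Progression of the cancer under study is not considered an adverse event unless it is considered to be drug related by the investigator".

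The protocol also describes drug effects that may resemble progression. Section 5.5 says that "cerebral edema could theoretically result as a consequence of pembrolizumab administration due to immune infiltration of the brain". Section 11.3.3 says immune effects may first appear as more enhancement and oedema, and that inflammatory imaging change may be wrongly taken for tumour growth.

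**The concern.** Toxicity is the first secondary objective (Section 1.3), and a reader of the final report will look to the death listing for fatal events. Whether a death enters that listing turns on the cause assigned to it. In an intracranial tumour treated with a checkpoint inhibitor, that cause can be hard to assign.

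The exemption works in one direction. A tumour death wrongly called drug related stays in the listing, where it can be questioned. A drug death wrongly called progression drops out, and nothing in the safety tables shows that it is gone. At stake is whether the fatal part of the toxicity result can be checked by someone who was not at the bedside.

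**Working it through.** **1. The plan's own figures.** The plan gives no figure for deaths or death reporting. Its one calculated figure is the power in Section 13.6: at least 10 successes in 24, null 26%, alternative 52%, one-sided 0.1. Exact binomial sums give P(X ≥ 10 | 24, 0.52) = 0.888 against the stated 88%, and P(X ≥ 10 | 24, 0.26) = 0.069. Both agree with the plan, and neither depends on how deaths are listed.

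**2. Where a death would appear, by attributed cause.**

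| Output | Cause other than progression, or progression considered drug related | Progression, not considered drug related |
|---|---|---|
| Adverse event summaries (7, 13.7) | Yes | Not the death; earlier recorded events yes |
| SAE report (7.3.1) | Yes; the 7.3.1 exemption itself does not repeat the drug-related exception | Exempt |
| Death listing (13.7) | Yes, if SAE-reportable | No |
| Overall survival (11.4.6) | Event | Event |
| PFS (11.4.6) | Event | Event, at progression or at death |
| PFS6 (13.2) | Failure if within six months of first treatment | Same |
| Off-study reason and date (5.14) | Recorded | Recorded |

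The gap is in the safety rows of the last column. It follows from combining Section 7, 7.3.1 and 13.7; no single section states it.

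**3. How a drug effect could be given that cause.**

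- Section 11.3.1.1 counts clinical worsening as progression unless it is clearly unrelated to the cancer. It also counts a patient who cannot return because of death or decline.
- Section 11.3.3 classes a patient with initial radiographic progression who then declines significantly as progressive, back-dated to the first such scan.
- Section 11.3.3 does not require a repeat scan in significant neurologic decline.
- Treatment may continue for up to three months while confirmation is awaited, so patients can be on drug during this period.

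Progression can therefore be declared without a confirming scan or histology.

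**4. Scale, under stated assumptions.** Assume all 26 accrued patients (Section 13.3) are treated. Use the two-sided 90% exact interval that 13.7 applies to toxicity proportions. For x = 0 the upper limit is 1 − 0.05^(1/26) = 0.109. For x > 0 the limits are the 5% quantile of Beta(x, 27 − x) and the 95% quantile of Beta(x + 1, 26 − x).

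| Fatal drug events (assumed) | Proportion | 90% interval |
|---|---|---|
| 0 | 0% | 0 to 10.9% |
| 1 | 3.8% | 0.2 to 17.0% |
| 2 | 7.7% | 1.4 to 22.3% |

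Let p be the true risk of a fatal drug event and m the share of such deaths attributed to progression. The chance that at least one occurs and none is listed is (1 − p(1 − m))^26 − (1 − p)^26. For p = 5% and m = one half this is 0.975^26 − 0.95^26 = 0.518 − 0.264 = 0.254.

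| p | m = 1/4 | m = 1/2 | m = 3/4 |
|---|---|---|---|
| 2% | 8% | 18% | 29% |
| 5% | 11% | 25% | 46% |
| 10% | 7% | 20% | 45% |

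The documents give no value for p or m. The table shows only that the omission would not be negligible if either were appreciable.

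**The case against.** The strongest reply is that the plan has several controls and that little would actually be lost.

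- **Earlier events are kept.** The exemption covers the death, not the events before it. Section 5.5 treats cerebral oedema as a gradable event. Grade 3 or higher neurologic toxicity is a named endpoint (13.2) with no relatedness condition, and non-fatal SAEs are listed by patient (13.7). This stands. A reader might infer that a fatal drug effect would vanish from the safety results altogether; the documents do not support that.
- **Misreading is guarded against.** Section 11.3.3 excludes T2/FLAIR change from radiographic progression for exactly this reason, provides for confirmation and encourages histology. Section 11.3.4 has all brain MRIs read centrally, and 11.3.1.1 excepts worsening clearly due to complications of therapy. These controls reduce the risk. They do not close the route through worsening enhancement followed by decline, and central review is described for scans, not for cause of death.
- **Other reporting rules apply.** Drug-related progression is an adverse event (Section 7), related SAEs are reportable at any time (7.3.1), Section 7.8.1 repeats no exemption, and 7.8.2 requires grade 5 events within 24 hours at any attribution. Each still needs the death to be called an adverse event or drug related first.
- **The link to deaths is inferred.** Section 5.5 calls drug-induced oedema theoretical, and 11.3.3 speaks of misread scans. This is correct. A reader might infer that fatal oedema is the toxicity most likely to be coded as progression; nothing in the documents establishes that.
- **Safety oversight continues.** Section 13.5 has no interim monitoring plan, but expedited reporting runs throughout. The point should not be read as saying that safety is unmonitored.

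**Conclusion.** The concern holds as a gap in the safety presentation. A death attributed to progression and not considered drug related is outside the adverse event definition, exempt under 7.3.1 and absent from the 13.7 listing. If the true cause was immune-related, the listing would err toward apparent safety. The death would remain in the survival endpoints, and anything recorded before it would remain in the toxicity tables.

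The size is unknown. One such death among 26 treated patients is the difference between 0% (0 to 10.9%) and 3.8% (0.2 to 17.0%), but no fatal-event rate is a planned estimate and no decision rule uses toxicity. The conclusion rests on reading Section 7, 7.3.1 and 13.7 together, and on the inference that a misread scan or decline can lead to a misattributed death. The primary analysis, sample size and power are unaffected. This is a cheap improvement, not a flaw in the design.

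**What to change.** In Section 13.7, list and tabulate every death among patients given at least one dose, from first dose to 90 days after last dose, whatever the attributed cause. Show for each:

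- date of death and days since last dose;
- attributed cause;
- the basis for it: last MRI, whether progression was confirmed, any recorded oedema, and histology where available.

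Then reconcile the introduction to Section 7, 7.3.1, 7.8.1, 7.8.2 and 13.7. Section 7.8.1 asks for any SAE within 90 days of the last dose without repeating the progression exemption, and its window differs from that in 7.3.1, which also ends at new anti-cancer therapy.

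I would not rewrite the SAE exemption itself. Limiting it to confirmed progression is tempting, but 11.3.3 waives repeat imaging in neurologic decline, so many ordinary tumour deaths could become reportable.

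The cost is one extra listing, and possibly a cause-of-death field and some abstraction from imaging and pathology reports, because survival follow-up alone does not supply the basis for attribution. No extra patients or scans are needed.
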